7.5 SECONDARY ENDPOINTS

7.5.1 Key secondary endpoint

This section is not applicable as no key secondary endpoint has been specified in the protocol.

7.5.2 Other secondary endpoints

Major bleeding events (MBEs)

MBEs will be analysed as time-to-event endpoint by Kaplan-Meier method using on-treatment analysis based on adjudicated data and treated set. The proportion of patients free from MBEs at the end of treatment period (84 days (Visit 8) or eEOT) will be provided by Kaplan-Meier estimates for the two treatment arms pooling all age groups. Due to the low event rate of major bleeding, age group stratification will not be considered. The confidence interval of proportion difference will be calculated based on Kaplan-Meier estimates and its variances.

Patients not having MBEs during the on-treatment period and patients who discontinue from the trial prematurely without having major bleeding events will be censored. For patients who have experienced more than one event during the trial, time to the first occurrence of the event will be used for analysis.

In case no MBE was observed in one of treatment arms, where the Kaplan-Meier estimate cannot be calculated, a descriptive table summarizing all MBEs will be provided.

PK/PD assessments

Analysis of standard PK/PD parameters will be performed according to 001-MCS-36-472_RD-01 on PKS, PDS, set as applicable (2).

Scheduled and unscheduled PK and PD data will be analysed separately. Only scheduled PK and PD data will be summarized descriptively. Unscheduled PK and PD data will be listed. As with unscheduled PK and PD data, PK and PD data collected at dose titration visits will be listed separately. The percentage of PK trough results (HPLC-MS/MS) within the target range of 50 to <250 ng/ml and outside target range at Visit 3, while at steady state (after at least six consecutive dabigatran etexilate doses), and following no more than one dose titration (again, at steady state (after at least 3 days following any dabigatran etexilate dose adjustment)) will be presented by formulation, by age group, and for patients treated with the capped dose and with the uncapped dose.

PK parameters: All concentrations will be listed and summarized descriptively. The concentrations will be compared descriptively with the exposure observed in adult patients or healthy subjects previously. PK data from this study along with data from other trials in the dabigatran program will be used to further refine the adult population PK model (7), allowing it to be used for the generation of predictions optimized for paediatric populations. The results of this model refinement will be reported separately.

PD parameters: The following descriptive statistics will be calculated for the PD parameters aPTT, ECT and any additional PD assay: these include, but are not limited to N, arithmetic mean, standard deviation, minimum, median, and maximum. Further, ratios to baseline (i.e. visit 2) for these parameters will be calculated and assessed by descriptive statistics. Dabigatran concentrations derived from dTT will be compared to dabigatran concentrations determined by HPLC-MS/MS. The comparison will be reported separately.

Dose adjustments, switch of therapy, and discontinuation of medication

The number and percentage of patients with dose adjustments (up-titration and down-titration separately), temporary and permanent discontinuation from therapy, and laboratory monitoring requirements for dose adjustment during the treatment phase will be summarized descriptively by treatment arm on treated set. For the DE arm, dose adjustments until the switch of therapy to SOC will be considered.

The number of laboratory monitoring requirements per patient for dose adjustment during treatment phase will be summarised by the number and percentage of patients requiring 1, 2, or more lab monitoring, as well as the mean, SD, min, median, and max of the number of lab monitoring requirements per patient. For the DE arm, lab monitoring requirements prior to the first switch, if any, to SOC will be counted only.

Frequency of patients switching the type of anti-coagulation therapy, including DE to SOC or change from one type of SOC to another (LMWH, VKA, and Fondaparinux) will be provided descriptively by treatment arm on treated set. For the DE arm, only the switch from DE to SOC will be counted, while for the SOC arm, all switches among SOC medication types will be counted. Reasons for switch of therapy from DE to SOC and among SOC types will be summarized. Frequency of DE treated patients with changes in dose and/or formulation type will also be summarized.

Permanent discontinuation from therapy and the reasons will be summarized in the disposition table.

Assessment of acceptability

Assessment of acceptability of an age-appropriate formulation at the end of therapy will be provided descriptively for DE treated patients.

Assessment of acceptability of capsules, pellets and OLF reconstituted with flavoured or unflavoured solvent at Days 3 (Visit 3), 21 (Visit 5) and 84 (Visit 8), or eEOT after randomisation will be summarized descriptively as well. Questions completed by investigator, by parent/legal guardian, and by patients (if old enough per investigator judgement) will be summarized descriptively.

Thrombus progression

Frequency of patients free from thrombus progression at day 84 ± 7 days after randomization (or eEOT, whichever comes first) will be analyzed descriptively by treatment arm and age group. Patients without VTE assessments by this time point will be summarized as well. Mortality related to VTE will be considered as recurrence of VTE.

All bleeding events and all-cause mortality

All adjudicated bleeding events and adjudicated all-cause mortality will be analyzed as time-to-event endpoint using stratified Cox proportional hazard model with treatment as a covariate in the model and age group as the stratification factor. A pooling of age groups might be necessary if no events were observed in certain age group.

Patients that do not experience any bleeding events will be included as censored observations at the date of patients' last visit, the date of death not related to bleeding, or the date of data cut-off, whichever comes first. Patients being alive at the end of observational period will be censored for all-cause mortality at the date of patients' last date known to be alive, or the date of data cut-off whichever comes first. All bleeding events and all-cause mortality based on treated set will be analysed descriptively and by Kaplan-Meier estimates for each treatment arm.

Incidence of bleeding events including MBEs, CRNM, minor bleeding events, and any bleeding events will be presented, as well as incidence of combined endpoint of major and CRNM bleeding events.

Components of efficacy endpoint

All components of the primary endpoint will be analyzed as proportions using adjudicated data as the primary analysis in [Section 7.4](#). Concordance between adjudicated events and investigator-reported events will also be summarized.

The proportion of patients achieving complete thrombus resolution at visit 8, the proportion of patients free from recurrent VTE, and the proportion of patients free from VTE-related death will be provided. Time to VTE-related death will be analyzed by Cox proportional hazard model with treatment as the covariate. Hazard ratio and p-value for the treatment in the model will be reported, and Kaplan-Meier estimates will be provided.

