2.2 TRIAL OBJECTIVES

The main objectives of this large phase IIb/III paediatric study are to assess the efficacy and safety of dabigatran etexilate relative to standard of care and to document the appropriateness of the proposed dabigatran etexilate dosing algorithm for use in patients from birth to less than 18 years of age.

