5.2 SAFETY

5.2.1 Endpoints of safety

The main safety endpoint, freedom from major bleeding events (MBEs), is defined as either fatal bleeding; clinically overt bleeding associated with a decrease in haemoglobin of at least 20 g/L in a 24-hour period; bleeding that is retroperitoneal, pulmonary, intracranial or otherwise involves the central nervous system; or bleeding that requires intervention in an operating suite.

Other safety endpoints:

Proprietary confidential information.

© 2019 Boehringer Ingelheim International GmbH or one or more of its affiliated companies. All rights reserved.

This document may not - in full or in part - be passed on, reproduced, published or otherwise used without prior written permission.

- Incidence of bleeding events including:
 - Major bleeding events; clinically relevant non-major bleeding events (CRNM), minor bleeding events and any bleeding events
 - Combined endpoint of major and CRNM bleeding events
- Incidence of adverse events, protocol-specified AESI and serious adverse events
- Treatment discontinuation due to an adverse event
- Change from baseline in safety laboratory values, vital signs and physical examination
- Global assessment of tolerability (measured as treatment discontinuation and adherence) to study medication

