7.3.2 Secondary analyses

Secondary analyses of primary endpoint

Proprietary confidential information.

© 2019 Boehringer Ingelheim International GmbH or one or more of its affiliated companies. All rights reserved.

This document may not - in full or in part - be passed on, reproduced, published or otherwise used without prior written permission.

Secondary analysis of the proportion of patients with complete thrombus resolution, with no recurrent VTE and no VTE-related death will consider age group as covariate and the treatment and age group interaction in a logistic regression model using ITT as the primary analysis.

Analyses of secondary endpoints

Major bleeding events will be analysed as time-to-event endpoint using Kaplan-Meier method. The proportion of patients free from major bleeding events at the end of planned treatment period (84 days (Visit 8) or eEOT) will be provided by Kaplan-Meier estimates for the two treatment arms pooling all age groups. Due to the low event rate of major bleeding, age group stratification will not be considered in the primary model for this endpoint. The confidence interval of proportion difference will be calculated based on Kaplan-Meier estimates and its variances. This safety analysis will be based on the treated set which will include events that occur between the date of first dose of study medication to the date of last dose of medication plus six-days (on treatment analysis). Patients who do not have major bleeding events during the treatment period and patients who discontinue from the trial prematurely without having major bleeding events will be censored. For patients who have more than one event during the trial, the time to the first occurrence of the event will be considered for the analysis.

Pharmacokinetic and pharmacodynamic analyses will be summarized in [Section 7.3.5](#) and [Section 7.3.6](#).

Frequency of dose adjustments, temporary and permanent discontinuation from therapy, number of laboratory monitoring requirements for dose adjustment during the treatment phase and frequency of switch of type of anti-coagulation therapy (including dabigatran to SOC) will be summarized descriptively for each treatment arm.

Freedom from thrombus progression at baseline will be summarized descriptively and for each treatment arm. Frequency of patients free from thrombus progression at day 84 after randomization (or eEOT, whichever comes first) will be analysed descriptively.

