4. CHANGES IN THE PLANNED ANALYSIS OF THE STUDY

Freedom from major bleeding events has been changed from the co-primary safety endpoint to a secondary endpoint, and major bleeding events have been removed from related null hypotheses in the primary analysis in the protocol amendment 6.

Other changes to the statistical analyses are described in protocol amendments. Please refer to latest protocol amendment (Amendment 9, dated 06Feb2019).

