6. GENERAL ANALYSIS DEFINITIONS

6.1 TREATMENTS

There are two treatment arms in the study: DE using a dosing algorithm or SOC. The assignment of treatment groups will be based on randomization for randomized patient set as defined in [Section 6.3](#). Patients will be allocated to one of the following treatments given below.

Table 6.1: 1 Labels of treatments for use in the Clinical Trial Report

Treatment	Long label	Short label
A	Dabigatran etexilate	DE
B	Standard of care	SOC

Patients switching from DE to SOC before the end of study will be considered as having treatment periods defined below. Patients switching from the original SOC treatment to another SOC will be considered as no change in the treatment group assignment.

The following periods will be defined:

- Screening: day of informed consent to the day prior to first administration of the trial treatment (DE or SOC)
- On-treatment: day of first administration of trial treatment to last administration of trial treatment + 6 days (residual effect period). This on-treatment period will be used for analysis of safety endpoints and adverse events (AEs), as specified in [Section 7.8.1](#).
- Post-treatment: end of on-treatment period +1 day up to day of the last follow-up visit, lost to follow-up, death, or consent withdraw regarding participation in the trial.
- Post-study: For patients not rolled over to the 1160.108 trial, it starts from last follow-up visit + 1 day up to end of the trial, i.e. the last contact/information received during the trial. For patients rolled over to the 1160.108 trial, it starts from last follow-up visit + 1 day in 1160.106 to the date of informed consent in 1160.108.
- Intention to treat: day of randomization up to Day 84 (+ 7), including all observed time on and off trial medication.
- Full follow-up: day of randomization up to day of the last follow-up visit, lost to follow-up, death, or consent withdrawn regarding participation in the trial.

Please note: for patients who had not reached the end of a treatment period as defined above at EMA interim data cut-off date, the respective treatment period ends at the cut-off date.

The screening, on-treatment, post-treatment, and post-study periods will be used for the summary and listings of AEs. The intention to treat, on-treatment, and full follow-up periods will be used for descriptive and statistical analysis of primary/secondary/further endpoints.

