2. Given minimized risk of not detecting recurrent VTE due to the study design, as well as the low incidence rate of recurrent VTE in the study population, we assume patients free from recurrent VTE until the presence of contradictory evidence - observed VTE recurrence.

Component 3: complete thrombus resolution

Assessment of index VTE status (best overall response) is scheduled on Day 84 ± 7 days (Visit 8) for patients who are alive without an early consent withdraw, regardless of the treatment status (completion or premature discontinuation) at that time.

- The thrombus status assessed at Day 84 ± 7 days will be used for evaluation of this component. If more than one thrombus assessment is available within this time window, the one closest to Day 84 will be adopted. Furthermore, if two index assessments performed within the time window were equally distant from Day 84 (e.g., an early assessment on Day 78 and a late assessment on Day 90), then the thrombus status after Day 84 will be adopted.
- For patients completing the treatment period OR patients terminating treatment early, if the index thrombus assessment during Day 84 ± 7 days is missing, but an early VTE assessment was performed, for instance, at an unscheduled visit or an eEOT visit, the latest available thrombus status will be carried forward (LOCF) in the primary analysis.
- If not any index VTE assessment was performed until Day 84 + 7 days, these patients will be considered as having missing data and NOT meeting the criterion of “complete thrombus resolution”.
- Patients with index VTE assessment performed only once after Day 84 + 7 days will be considered to have missing data and to not achieve the complete thrombus resolution in the primary analysis,

Age group will be used as stratification factor using a Mantel-Haenszel type weighted average of differences with weights as proposed by Greenland and Robins [R09-1299] (3).

The testing hypotheses for the non-inferiority and superiority of the primary endpoint are:

$H_{01}: p_{IC} - p_{ID} \geq 20\%$ vs. $H_{11}: p_{IC} - p_{ID} < 20\%$, where p stands for the proportion of patients meeting the primary endpoint, the subscript C for SOC, and D for dabigatran etexilate.

$H_{03}: p_{IC} - p_{ID} \geq 0$ vs. $H_{13}: p_{IC} - p_{ID} < 0$.

The details of Cochran-Mantel-Haenszel test and SAS code are provided in [Section 9.4](#).

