7.7 EXTENT OF EXPOSURE

Only descriptive statistics are planned for this section of the report. Summaries will be provided for treated set. Total exposure (in days) is defined as date of last administration of DE/SOC – date of first administration of DE /SOC + 1, ignoring the temporary interruptions, i.e. intermittent off-treatment periods were considered in the extent of exposure.

For DE treated patients, listings on exposure, including the actual treatment received, starting dose, formulation type, dates of first and last doses, the total treatment time, whether a dose adjustment was done, whether patient switched to SOC, and reason for change will be provided.

For SOC treated patients, listings on exposure, including the SOC treatment type, medication name, dates of first and last doses, the total treatment time, whether a SOC change was done, and reason for change will be provided.

Dose adjustment, interruption and discontinuation are analysed as secondary endpoints and specified in [Section 7.5](#).

The number and percentage of patients with DE trough plasma concentrations in the target range (50 to < 250 ng/mL) and outside target range while on treatment will be presented.

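### SAP 7.5.2 wrongly treats the Kaplan-Meier estimate as incalculable when an arm has no major bleed, and no visible text pre-specifies a between-arm interval that works at zero events

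*SAP*

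**What the plan says.** Protocol 2.2 sets out to "assess the efficacy and safety of dabigatran etexilate relative to standard of care". Protocol 5.2.1 begins "The main safety endpoint, freedom from major bleeding events (MBEs" and then defines the events. SAP 4 records that "Freedom from major bleeding events has been changed from the co-primary safety endpoint to a secondary endpoint"; no hypothesis is attached to it now.

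The planned comparison is the same in both documents. KM estimates of freedom from MBE are given per arm, age groups pooled, on the treated set. Protocol 7.3.2 continues: "The confidence interval of proportion difference will be calculated based on Kaplan-Meier estimates and its variances". Neither document states a confidence level for this interval.

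SAP 7.5.2 adds an exception that protocol 7.3.2 does not contain: "In case no MBE was observed in one of treatment arms, where the Kaplan-Meier estimate cannot be calculated, a descriptive table" summarising the MBEs is to be provided. The exception speaks of one arm; both arms at zero is not named.

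Elsewhere, SAP 7.5.2 plans to present MBE incidence, with no interval. The Cox models in protocol 7.3.2 and 7.3.3 and in SAP 7.5.2 cover all bleeding, major plus clinically relevant bleeding, and mortality, but not MBE alone. A Newcombe-Wilson interval is named in protocol 7.6, but only for the efficacy endpoint in the power table.

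**The concern.** The exception rests on a technical mistake, and the mistake hides the real difficulty. The point estimate exists in a zero-event arm. It is the variance that fails, and with it the interval for the difference. Because the SAP places the problem in the estimate, it withdraws a number that could be reported and does not replace the interval that could not.

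At stake is the main safety comparison. If an arm has no MBE, the report will hold counts and percentages but no pre-specified statement of how large an excess in major bleeding the data rule out. Any interval added later would be chosen after the counts are known, in a trial where only the adjudication committee is blinded (protocol 4.1.5.1).

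**Working it through.** **Plan's own figure.** The documents give no power, margin or expected width for MBE. The only sizing figure that can be checked is the primary power. Simulating the formula in protocol 7.6 (94 and 47 patients, 72% in both arms, 20% margin, z = 1.64) gives 81.8% against the stated 82%. This confirms the arm sizes used below.

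**1. KM in a zero-event arm.** S(t) is the product of (1 - d/r) over event times. With no event times the product is empty, so S(84) = 1. Greenwood's variance is S² × Σ d/[r(r - d)], an empty sum, so it is 0. The estimate is 100% and that arm adds no uncertainty to the interval.

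**2. How often an arm has no events.** Inputs: 94 and 47 patients (protocol synopsis); 0.5% to 1.7% (protocol 2.3, no time base stated); 5.6% and 12.5% (the randomised paediatric study in protocol 1.1). Assumptions: equal rates in both arms and complete on-treatment follow-up. P(no events in an arm) = (1 - p)^n, and P(at least one zero arm) = A + B - AB, with A and B the two arm values.

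| Risk p | A, n = 94 | B, n = 47 | At least one zero arm | Both zero |
|---|---|---|---|---|
| 0.5% | 0.624 | 0.790 | 92% | 49% |
| 1.0% | 0.389 | 0.624 | 77% | 24% |
| 1.7% | 0.200 | 0.447 | 56% | 9% |
| 5.6% | 0.004 | 0.067 | 7% | 0.03% |
| 12.5% | <0.001 | 0.002 | 0.2% | <0.01% |

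If 0.5% to 1.7% is instead a yearly rate, the 90-day risk 1 - (1 - r)^(90/365.25) is 0.12% to 0.42%, and the chance of a zero arm is 99% to 94%. Since 141 is a minimum: at 120 and 60 patients it is 88% to 44% over 0.5% to 1.7%.

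**3. What a valid interval would say.** Differences are dabigatran minus SOC in MBE risk. For 0/n, the Wilson upper limit is z²/(n + z²). The Newcombe limits at 0/94 versus 0/47 are therefore:

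- 95% (z = 1.96, z² = 3.842): lower -3.842/50.842 = -7.6 points; upper 3.842/97.842 = +3.9 points.
- 90% (z = 1.645, z² = 2.706): lower -2.706/49.706 = -5.4 points; upper 2.706/96.706 = +2.8 points.

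Both levels are assumptions, since none is given for MBE; the primary analysis uses 90%. Miettinen-Nurminen at 95% gives -7.6 to +4.0. The KM-variance interval here has zero width.

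**4. Event windows.** Any replacement must say which events count, and the documents differ.

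- Protocol 7.3 ends the treated-set window at Visit 8, with 6 days after the last dose only for patients who stop prematurely.
- Protocol 7.3.2 counts MBE to the last dose plus six days for everyone.
- SAP 6.1 agrees with 7.3.2: "On-treatment: day of first administration of trial treatment to last administration of trial treatment + 6 days (residual effect period".
- SAP 7.7 exposure stops at the last dose: "Total exposure (in days) is defined as date of last administration of DE/SOC" minus the date of first administration, plus 1. It leaves out the 6 residual days.

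**5. Cost of a crude proportion.** It ignores unequal on-treatment time. Assume 15% stop dabigatran early (the ceiling in protocol 7.6), none stop SOC, hazards are equal and constant, and completers contribute 84 + 6 = 90 days. If stops fall on days 5 to 20, stoppers contribute about 12.5 + 6 = 18.5 days. Mean dabigatran time is 0.85 × 90 + 0.15 × 18.5 = 79.3 days, a ratio of 0.88. At a 1.7% risk the difference is biased by about 1.7 × (0.88 - 1) = -0.2 points. If SOC stops early as often and in the same pattern, the bias is about 0.

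**The case against.** The strongest reply is that the SAP does the safe thing for a misworded reason. With a zero arm it withholds the KM-variance interval, so it does not publish a misleading one. That stands. A reader might infer that the plan would report an interval that under-covers. Nominal 95% coverage of the KM-variance interval would indeed be 84% at 1.7% on dabigatran versus 0.5% on SOC, and 55% the other way round, but only if it were computed despite the fallback. Among outcomes with events in both arms, where the SAP does plan it, coverage in those two scenarios is about 99.98%.

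A reader might also infer an undeclared departure from the protocol, because SAP 4 does not list the exception. The documents do not support that. Protocol 7.3.1 leaves further detail to the SAP, SAP 3 describes itself as an elaboration of the protocol, and the SAP history table logs that the MBE analysis was added to 7.5.2.

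Third, MBE was moved to secondary on regulatory advice (protocol section 11, amendment 06), and protocol 7.3.3 calls the safety analyses descriptive. Counts and percentages will be reported, so anyone can compute an interval. That stands too: the loss is of pre-specification, not of data.

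Fourth, zero arms may be rare. At the rates in protocol 1.1 they would be, and nothing in the documents settles which rates apply.

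**Conclusion.** The point holds, as a minor one. The statement in SAP 7.5.2 is wrong: a zero-event arm has a KM estimate of 100%, and it is the variance that fails. No visible text supplies a between-arm MBE interval valid in that case. Parts of the SAP are not in the supplied text (SAP 7.4 says "The details of Cochran-Mantel-Haenszel test and SAS code are provided in" Section 9.4, which is absent), so the claim is limited to what can be seen.

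The chance that the fallback applies runs from about 99% to 0.2% across the documents' own rates and the possible time bases. It would be going too far to say that it will usually apply. With no events in either arm, a valid interval would still leave open an excess on dabigatran of up to 3.9 points (95%) or 2.8 points (90%), which a table of zeros does not show. These figures assume 94 and 47 patients with complete follow-up, and the zero-arm chances also assume equal rates. No hypothesis test and no part of the primary conclusion depends on this.

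**What to change.** In SAP 7.5.2:

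1. Delete the statement that the estimate cannot be calculated, and report KM = 100% for an arm with no MBE. Cover the case of both arms at zero.
2. Name one leading between-arm interval for the MBE risk difference, Newcombe or Miettinen-Nurminen, at a stated confidence level, reported whatever the counts. Keep the KM difference as supportive when both arms have events.
3. State one event window, after reconciling protocol 7.3 with protocol 7.3.2 and SAP 6.1.
4. Show exposure-adjusted MBE rates over that same window, not over the SAP 7.7 exposure.

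The cost is a few lines of SAP text, one extra interval and one rate line. The downside is the crude proportion's blindness to unequal time on treatment: about 0 to -0.2 points at a 1.7% risk on the assumptions above, small beside the interval widths and visible in the exposure-adjusted rates.

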7.3 PLANNED ANALYSES

The following analysis populations will be defined:

The randomized set (RS) will include all randomized patients in the treatment groups to which they are randomized. The intent-to-treat (ITT) principle will be applied to the randomized set including events from the time of randomization to the time point of interest (e.g. visit 8 for the primary efficacy endpoint). Patients who terminate the study medication prematurely will be followed and the events which occur after premature discontinuation of medication and before the time point of interest will be included in the analysis using the randomized set.

Proprietary confidential information.

© 2019 Boehringer Ingelheim International GmbH or one or more of its affiliated companies. All rights reserved.

This document may not - in full or in part - be passed on, reproduced, published or otherwise used without prior written permission.

The treated set (TS) will include all patients who are dispensed study medication and are documented to have taken at least one dose of study medication in the treatment groups according to their initial treatment. The analyses using the treated set will include the efficacy and safety endpoint events which occur from the date of first drug administration to visit 8 or date of last drug administration + 6 days if discontinued prematurely.

The pharmacokinetic set (PKS) will include all treated patients with at least one PK/PD measurement and having no protocol violations relevant to the evaluation of PK or PD endpoints.

More details will be specified in the TSAP.

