Under the assumption that the true unknown complete thrombus resolution rate is 72% of both dabigatran and SOC, the proposed sample size of 141 is sufficient to demonstrate non-inferiority with adequate power (82%).

If the complete thrombus resolution rate in dabigatran is truly lower than the SOC, the chance of showing non-inferiority drops to 33% when the difference is 10% (complete thrombus resolution rate 62% vs 72% for dabigatran and SOC, respectively), and to below 5% when the non-inferiority margin of 20% is reached (complete thrombus resolution rate 52% vs 72% for dabigatran and SOC, respectively).

However, the most likely scenario for the paediatric population is to assume similar thrombus resolution rates with both dabigatran and SOC, based on the following considerations: primary efficacy results obtained from adult VTE RE-COVER-trials ([P13-16985](#)) demonstrated robust non-inferiority. In addition, it is the expectation that the gMean trough concentration in the paediatric trials will exceed the average trough exposure of RE-COVER due to the option of up-titration of the dose if initial exposure is < 50 ng/ml compared to fixed dosing in the adult trials. Therefore the Sponsor considers the sample size and 20% margin are reasonably sensitive to evaluate non-inferiority in the paediatric population. See Table 7.6: 3 for summary.

Proprietary confidential information.

© 2019 Boehringer Ingelheim International GmbH or one or more of its affiliated companies. All rights reserved.

This document may not - in full or in part - be passed on, reproduced, published or otherwise used without prior written permission.

Table 7.6: 3 Summary of power estimates for the primary endpoint with a sample size of 141

One-sided confidence level	Primary endpoints (non-event rate)	True rate difference	Margin for rate difference	Power [#]
90%	72%	0.0%	20%	82%
95%	72%	0.0%	20%	71%

[#] Power for the non-inferiority approach is computed as the proportion of 100,000 simulations in which the observed upper bound of one-sided confidence intervals for $p_{1C} - p_{1D}$ and $p_{2C} - p_{2D}$ (assuming 94 and 47 evaluable patients in dabigatran arm and control arm, respectively) are below the specified equivalence margin. The confidence interval for the VTE endpoint is estimated by Newcombe-Wilson method ([R08-4386](#)).

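### The zero-event rule for major bleeding in SAP 7.5.2 rests on a false premise and in effect removes the only named between-arm interval if an arm has no event

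*SAP*

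**What the plan says.** Protocol 5.2.1 makes freedom from MBE the main safety endpoint, and Protocol 2.2 makes safety relative to standard of care (SOC) a main objective. Since Amendment 6 it has been a secondary endpoint with no hypothesis (SAP 4).

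Protocol 7.3.2 plans a Kaplan-Meier analysis on the treated set, pooled over age groups, and then: "The confidence interval of proportion difference will be calculated based on Kaplan-Meier estimates and its variances". It makes no exception for an arm without events. SAP 7.5.2 repeats this plan: "The proportion of patients free from MBEs at the end of treatment period (84 days (Visit 8) or eEOT) will be provided by Kaplan-Meier". There too, the interval comes from those estimates and their variances. The SAP gives the reason for pooling: "Due to the low event rate of major bleeding, age group stratification will not be considered". It then adds the rule at issue: "In case no MBE was observed in one of treatment arms, where the Kaplan-Meier estimate cannot be calculated, a descriptive table summarizing all MBEs". That table is the only output stated for this case.

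Neither section gives a confidence level. SAP 7.5.2 separately has the incidence of MBEs presented, without naming an interval.

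**The concern.** The rule gives the wrong reason for the failure, and so chooses the wrong remedy. If nobody in an arm bleeds, the survival curve stays at 1 and the estimate is 100%. What degenerates is the variance of that estimate, which becomes 0. Only the interval method needs changing, yet the stated output falls back to a table.

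At stake is the statement of uncertainty for the main safety endpoint. A bare 2 against 0, or 0 against 0, is easily over-read in a trial of this size. Without a planned method, the team either reports no interval, uses one that treats the zero-event arm as known without error, or chooses one after seeing the data of an open-label trial.

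**Working it through.** **Inputs**
- Arm sizes 94 and 47: Protocol 7.6.
- MBE risk 0.5% to 1.7% of patients: Protocol 2.3, a literature range in the benefit-risk text.
- MBE risk 5.6% (2/36) and 12.5% (5/40), pooled 7/76 = 9.2%: Protocol 1.1, the trial of a low molecular weight heparin against heparin followed by a vitamin K antagonist.
- Assumptions: 95% level; independent binomial counts; no early censoring, so that the Kaplan-Meier variance equals the binomial one.

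**The plan's own figure.** The documents give no operating figure for MBE. As a check on the arm sizes, exact enumeration of the power rule in Protocol 7.6 at 72% in both arms gives 81.8%, against 82% stated.

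**How often an arm has no MBE.** P(at least one arm with none) = 1 - [1 - (1 - pD)^94] × [1 - (1 - pC)^47], where pD and pC are the dabigatran and SOC risks.

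| Risk, dabigatran / SOC | No MBE, dabigatran | No MBE, SOC | At least one arm |
|---|---|---|---|
| 0.5% / 0.5% | 0.624 | 0.790 | 92% |
| 1.0% / 1.0% | 0.389 | 0.624 | 77% |
| 1.7% / 1.7% | 0.200 | 0.447 | 56% |
| 1.7% / 0.5% | 0.200 | 0.790 | 83% |
| 0.5% / 1.7% | 0.624 | 0.447 | 79% |
| 5.6% / 5.6% | 0.004 | 0.067 | 7% |
| 9.2% / 9.2% | 0.0001 | 0.011 | 1.1% |
| 5.6% / 12.5% | 0.004 | 0.002 | 0.6% |

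For the first row: 1 - (1 - 0.624)(1 - 0.790) = 0.921. The expected total number of MBEs is 141 × 0.005 = 0.7 and 141 × 0.017 = 2.4 at the ends of the low range. If the SAP's trigger is read as exactly one arm with none, the probability is 43%, 53% and 47% at 0.5%, 1.0% and 1.7%, and the case of none in both arms is then not covered at all.

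**What the interval would show** (dabigatran minus SOC, percentage points)
- Zero-variance interval for 2/94 against 0/47: 2.13 ± 1.96 × sqrt(0.0213 × 0.9787 / 94) = -0.8 to +5.0. The 47 SOC children contribute no uncertainty.
- Newcombe interval for the same data. The Wilson limits are 0.59% to 7.43% for 2/94, and 0% to 7.56% for 0/47. Lower limit: 2.13 - sqrt((2.13 - 0.59)² + 7.56²) = -5.6. Upper limit: 2.13 + (7.43 - 2.13) = +7.4.
- Newcombe for other counts: 0/94 against 0/47, -7.6 to +3.9; 1/94 against 0/47, -6.5 to +5.8; 0/94 against 1/47, -11.1 to +2.2.

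**Should the method switch only at zero?** Newcombe for 1/94 against 0/47 is 12.3 points wide. The Kaplan-Meier interval for 1/94 against 1/47 is -5.7 to +3.6, or 9.2 points wide before rounding the limits. Under a switching rule, one more event would narrow the interval. Newcombe for 1/94 against 1/47 is -10.1 to +4.0, so reporting it in every case avoids the jump.

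**The case against.** The strongest reply is that nothing hangs on this interval. MBE has no test, Protocol 7.3.3 calls the safety analyses descriptive, counts by arm are still shown, and MBEs enter the Cox models for all bleeding and for major plus clinically relevant bleeding. Any reader can compute an interval from the counts. This limits the consequence, and I accept it. It does not rescue the rule: an interval is itself description, the protocol already plans one, and the Cox models mix MBEs with other bleeds.

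Three stronger readings are tempting, and the documents do not support them.
- A reader might infer that the SAP expressly cancels the interval. It does not. The loss follows because the only interval named rests on an estimate that the SAP declares unavailable. Nor does the SAP contradict the protocol: it adds a case the protocol did not address.
- A reader might take 56% to 92% as the trial's expected frequency. It is conditional. The 0.5% to 1.7% range is background literature, not a planning assumption for MBE, and the paediatric trial in Protocol 1.1 had much higher rates.
- A reader might conclude that no other MBE comparison exists. Some sections, such as SAP 9, are not in the public text, so that cannot be said.

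It is also fair to object that the protocol's mention of a Newcombe method, "The confidence interval for the VTE endpoint is estimated by Newcombe-Wilson method", belongs to a power-table footnote. It shows that the sponsor knows the method, not that it is a planned analysis of MBE.

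**Conclusion.** The point holds in limited form. The SAP's reason is technically wrong, and following it would needlessly give up the uncertainty statement for the main safety endpoint. With 94 and 47 treated children, the trigger is met with probability 56% to 92% if MBE risk is 0.5% to 1.7%, and about 0.6% to 7% at the rates of the trial in Protocol 1.1. It therefore matters if rates are low, which SAP 7.5.2 expects. Where it applies, the choice is between no planned interval and one that is too narrow. These figures assume independent counts, full follow-up and a 95% level. This is worth correcting, but it is a secondary endpoint with no hypothesis test, and no primary inference changes.

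**What to change.** In SAP 7.5.2:
- Delete the clause saying that the Kaplan-Meier estimate is not calculable, and state that it is reported as 100% when an arm has no event.
- Pre-specify a 95% Newcombe interval for the difference in the proportion of treated children with an on-treatment MBE. Report it whatever the event counts, next to the Kaplan-Meier interval where that is estimable, and with the table of all MBEs.
- Name the counting window. SAP 6.1 has "On-treatment: day of first administration of trial treatment to last administration of trial treatment + 6 days (residual effect period"), whereas Protocol 7.3 counts treated-set events "to visit 8 or date of last drug administration + 6 days if discontinued prematurely", which ends at Visit 8 for completers.
- Show person-time or discontinuations by arm beside the interval.

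The cost is SAP wording and one extra procedure call, with no new data or visits. Two downsides should be stated. First, the interval is wide and conservative (coverage 99.9% at 0.5% and 98.8% at 1.7% risk in both arms), so it cannot establish safety. Second, crude proportions count children who stop early as event-free afterwards. This may differ by arm, because Protocol 3.3.4.1 and 4.1.3 require dabigatran to stop when trough levels stay out of range after one adjustment, while Protocol 4.1.4 does not treat a change of SOC type as discontinuation. That is why follow-up by arm belongs beside the interval.
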